#### **5. Recruitment Model:**

The recruitment for the project will be conducted by the researchers involved, and the selection of participants will be voluntary and carried out on a convenience basis, in a non-random manner.

In all cases, the referred participant must give prior informed consent for referral, by signing the informed consent form and verifying that they meet the inclusion criteria and none of the exclusion criteria.

---

#### **6. Informed Consent:**

In accordance with the provisions of the Clinical Research Law (Law No. 21/2014 of April 16, amended by Law No. 73/2015, July 27), the researcher will provide the informed consent document to the volunteer. The information will be provided verbally and in writing, in accessible language, and the volunteer will be given time to read the document and ask any questions.

It will be ensured that the participant receives the appropriate information to consent to the research procedures, preserving their autonomy and decision-making power regarding participation. All information about the project, including its objectives, procedures, participant duties and rights, risks and benefits, data handling, civil liability insurance, as well as the contact person's details, will be included.

The informed consent will be signed by the volunteer if they agree to participate, and by the researcher, in duplicate, with one copy for the participant and another for the researcher. The participant can withdraw their informed consent for participation in the project at any time, by notifying a member of the research team, preferably in writing, without the need for justification, without incurring any form of liability, and without suffering any harm. If the participant withdraws their consent, all data collected about that participant will be excluded, respecting the right to be forgotten.

---

## **7. Participant Confidentiality:**

The participant will not be identified by any of their personal data. To ensure the anonymization of the data collected during the study, each participant will be assigned an identification number, consisting of an alphanumeric code with 3 digits: the first digit corresponds to one of three letters identifying the interview location: A (HDM), B (HSA), C (CS7R), while the last two digits correspond to a sequential number for the participant, starting from 01. In the case of participants being "re-tested," the code will include an apostrophe after the letter.

In all documents, databases, or others, the participant's information will only be identified by this alphanumeric code.

Only the Principal Investigator will have access to the list that links the identification number to the participant's personal data. This list will be in electronic format with restricted access permissions, preventing unauthorized individuals from accessing, printing, forwarding, or copying confidential information.

---

## **8. Process Implementation:**

- Provision of "Link" at the selected data collection units the materials (questionnaires, informed consents, and envelopes).
- Distribution of data collection materials to data collection units by colleagues interested in collaborating.
- Identification of participants in the clinic, either because they express complaints or through regular medical history taken during consultation.
- Invitation to identified participants to complete the questionnaire in the nearest waiting room, in a more private space designated for the process.
- Sealing of the envelope in person in the consultation room and placing it in a closed box with a slot for insertion.
- Return of completed questionnaires to the Principal Investigator.

---

## **9. Data Collection Method:**

After voluntary recruitment and confirmation of inclusion criteria and the absence of exclusion criteria, the possibility of inclusion in the study and the volunteer's willingness to participate will be certified. The Informed Consent Form will be provided for the participant to read carefully, while being verbally informed about the details of the study. Once consent is obtained, the participant will complete the form, which will include the participant ID according to a sequential number assigned to each participant. A researcher will be available for any clarification needed during the self-completion of the form.

---

#### **10. Participant Benefits:**

The participant will not receive any individual benefits apart from the opportunity to participate in the study and the chance to raise and clarify any concerns regarding this specific and sensitive health issue (female genital atrophy). However, their participation in this research project may help other patients receive better healthcare in the future. The participant will have the right to request, in writing, the final publication results from the Principal Investigator.

---

#### **11. Data Review and Database Management:**

This project complies with the legal provisions and regulations applicable, namely, the Clinical Research Law No. 21/2014 of April 16 in its current version, Law No. 12/2005 of January 26 ("Genetic and personal health information"), the General Data Protection Regulation, as well as international Good Clinical Practice (GCP) guidelines (International Conference on Harmonization).

Signed informed consents will be stored in a secure physical location with restricted access specifically for that purpose. The student/Principal Investigator will be responsible for entering data into the digital data files (DDF), which will be stored in a specific physical location with restricted access. The data from the DDF will be transferred by the student/Principal Investigator into a global electronic database, which is secure and has restricted access, ensuring that the data is entered completely and accurately. Personal data collected within the framework of this research project and shared between FMUM/ICVC, IPL/ciTechCare, and the Sete Rios Health Center will be kept in secure files, with restricted access, whether electronic or physical, for 15 years after the completion of the study, in compliance with current legislation. The personal data identifying the participants (list linking the participant's name to the alphanumeric identification code) will only be kept by the Principal Investigator in a secure location, and only the investigator will have access to their identity.

The personal data of participants and researchers and the electronic databases will only be accessible to authorized members of the research team. Additionally, study data may be communicated to the competent Ethics Committees and other entities under the relevant clinical trial legislation, who may have access to this data. It will be ensured that all individuals or entities with access to personal data are bound by confidentiality agreements.

The electronic data will have restricted access permissions to prevent unauthorized persons from accessing, printing, forwarding, or copying confidential information.

## **12. Statistical Analysis:**

An anonymized data sheet will be constructed for statistical treatment to validate the questionnaire by determining its reliability and validity using appropriate statistical methods.

---

## **13. Ethical Considerations:**

This study will be approved by the Administration Council and the Ethics Committee of CHL-HSA, the clinical directors of HDMA and UCSP Sete Rios, as well as the Ethics Committee of the Lisbon and Tagus Valley Regional Health Administration. This clinical study has been designed, and will be implemented, executed, and reported in accordance with the current and future amendments of the International Conference on Harmonization – Good Clinical Practice (ICH-GCP) guidelines, laws, regulations, and ethical codes applicable to the locations where the clinical study is conducted, including but not limited to Law No. 21/2014, of April 16, and all decisions and instructions from relevant authorities, boards of directors, and/or ethics committees. All participants will be informed and clarified about the procedures, study objectives, and data confidentiality. It will be ensured, prior to data collection, that participation in the study is voluntary and informed, and that all participants will be guaranteed the right to withdraw from the study at any time, without any penalties. All participants will sign the Informed Consent Form, which will be provided in duplicate, one for the participant and the other for inclusion in the project. To ensure ethics in data collection, the questionnaires used in the study will be given to participants in envelopes, which will be sealed in the participant's presence.

It is emphasized that there are no direct risks from participating in the study that need to be disclosed.

---

## **14. Publication of Results:**

The dissemination of the study results is part of the research project process, with the confidentiality and privacy of the participants' personal data ensured, guaranteeing that their identification will not be possible, regardless of the form of result dissemination. This is an academic study of a non-commercial nature.

---

## **15. Funding:**

The research project budget will be funded by financial instruments in the health sector, which are being identified for application, with funding already guaranteed for materials, data transportation logistics, and postage. No additional costs are expected for the involved entities, including UCSP Sete Rios, HSA, or HDMA, particularly no extra costs for the working hours of the staff involved in the study.

---

## **16. Timeline:**

The proposed work plan for this research project, to be carried out in the year 2022, involves the following work plan and schedule:

### **Tasks**

- **Literature Review**

2022	2023	2024	2025

- **Translation and Cultural Adaptation:** January to April 2022
- **Presentation of the Study to Participating Health Units:** April to June 2022
- **Protocol Instruction to the Ethics Committees:** June to September 2022
- **Conducting the Study with Participants:** October 2022 to January 2024
- **Development of the Digital Database and Statistical Data Analysis:**

2023	2024	2025

- **Scientific Dissemination of the Data:** From 2025

## Annex 1: Portuguese Version of DIVA Questionnaire

### QUESTIONÁRIO DE IMPACTO DO ENVELHECIMENTO VAGINAL NO DIA-A DIA COD:.....

Estamos interessados em entender o impacto dos sintomas vaginais como: secura vaginal, dor, irritação e comichão no seu dia-a-dia. Para cada pergunta abaixo, marque a resposta que melhor descreve como as suas atividades, relacionamentos e sentimentos foram afetados por qualquer um destes sintomas durante as últimas 4 semanas.

#### **Parte A. Durante as últimas 4 semanas, quanto é que os sintomas vaginais como: secura, ardor, irritação ou comichão, foram desconfortáveis ou interferiram na sua capacidade de:**

1. Andar á velocidade habitual?

0 Nada   1 Um pouco   2 Moderadamente   3 Bastante   4  
Extremamente

2. Usar a roupa e lingerie que quer?

0 Nada   1 Um pouco   2 Moderadamente   3 Bastante   4  
Extremamente

3. Usar a casa de banho ou limpar-se após o uso desta?

0 Nada   1 Um pouco   2 Moderadamente   3 Bastante   4  
Extremamente

4. Ficar sentada mais de 1 hora?

0 Nada   1 Um pouco   2 Moderadamente   3 Bastante   4  
Extremamente

5. Ter uma boa noite de sono?

0 Nada   1 Um pouco   2 Moderadamente   3 Bastante   4  
Extremamente

#### **Parte B. Durante as últimas 4 semanas, com que frequência os sintomas vaginais como: secura, ardor, irritação ou comichão, fizeram com que se sentisse:**

6. Deprimida ou em baixo?

0 Nunca   1 Raramente   2 Às vezes   3 Frequentemente   4 Quase sempre

7. Embaraçada?

0 Nunca   1 Raramente   2 Às vezes   3 Frequentemente   4 Quase sempre

8. Frustrada ou ressentida?

0 Nunca  1 Raramente  2 Às vezes  3 Frequentemente  4 Quase sempre

9. Mal consigo própria?

0 Nunca  1 Raramente  2 Às vezes  3 Frequentemente  4 Quase sempre

**Parte C. As perguntas que se seguem são sobre o impacto dos seus sintomas, nas relações sexuais e outros tipos de atividade sexual, como autoestimulação ou masturbação. Durante as últimas 4 semanas, sintomas vaginais como: secura, ardor, irritação ou comichão, afetaram:**

10. O seu desejo ou interesse em ter relações sexuais ou outros tipos de atividade sexual (autoestimulação ou masturbação)?

0 Nada  1 Um pouco  2 Moderadamente  3 Bastante  4 Extremamente  
 Não aplicável- não tive atividade sexual de nenhum tipo recentemente.

11. A frequência com que teve relações sexuais, ou outros tipos de atividade sexual (incluindo autoestimulação ou masturbação)?

0 Nada  1 Um pouco  2 Moderadamente  3 Bastante  4 Extremamente  
 Não aplicável- não tive atividade sexual de nenhum tipo recentemente.

12. A sua capacidade de ficar excitada durante a atividade sexual (incluindo autoestimulação ou masturbação)?

0 Nada  1 Um pouco  2 Moderadamente  3 Bastante  4 Extremamente  
 Não aplicável- não tive atividade sexual de nenhum tipo recentemente.

13. A sua capacidade de espontaneamente se dedicar á atividade sexual (incluindo autoestimulação e masturbação)?

0 Nada  1 Um pouco  2 Moderadamente  3 Bastante  4 Extremamente  
 Não aplicável- não tive atividade sexual de nenhum tipo recentemente.

14. A sua capacidade de relaxar e desfrutar da atividade sexual (incluindo autoestimulação ou masturbação)?

0 Nada    1 Um pouco    2 Moderadamente    3 Bastante    4 Extremamente

Não aplicável- não tive atividade sexual de nenhum tipo recentemente.

15. O nível de prazer que experienciou durante a atividade sexual (incluindo autoestimulação ou masturbação)?

0 Nada    1 Um pouco    2 Moderadamente    3 Bastante    4 Extremamente

Não aplicável- não tive atividade sexual de nenhum tipo recentemente.

16. O seu desejo ou interesse em ter um relacionamento sexual?

0 Nada    1 Um pouco    2 Moderadamente    3 Bastante    4 Extremamente

Não aplicável- não tive atividade sexual de nenhum tipo recentemente.

17. A sua confiança em ser capaz de satisfazer sexualmente um parceiro(a)?

0 Nada    1 Um pouco    2 Moderadamente    3 Bastante    4 Extremamente

Não aplicável- não tive atividade sexual de nenhum tipo recentemente.

18. A sua satisfação geral com a sua vida sexual?

0 Nada    1 Um pouco    2 Moderadamente    3 Bastante    4 Extremamente

Não aplicável- não tive atividade sexual de nenhum tipo recentemente.

**Parte D. As afirmações que se seguem descrevem a forma pela qual os seus sintomas vaginais podem ter afetado o que sente por si e pelo seu corpo. Por favor, indique o quão verdadeira cada uma das seguintes afirmações foi para si durante as últimas 4 semanas.**

19. Os meus sintomas vaginais fazem sentir-me como se estivesse a envelhecer.

0 Nada    1 Um pouco    2 Às vezes    3 Muitas vezes    4 Sempre

20. Sinto-me indesejável devido aos meus sintomas vaginais.

0 Nada   1 Um pouco   2 Às vezes   3 Muitas vezes   4 Sempre

21. Quando penso nos meus sintomas vaginais, sinto como se tivesse perdido algo.

0 Nada   1 Um pouco   2 Às vezes   3 Muitas vezes   4 Sempre

22. Os meus sintomas vaginais fazem-me sentir como se o meu corpo se estivesse a deteriorar

0 Nada   1 Um pouco   2 Às vezes   3 Muitas vezes   4 Sempre

23. Sinto-me menos sexualmente atraente (sexy) devido aos meus sintomas vaginais.

0 Nada   1 Um pouco   2 Às vezes   3 Muitas vezes   4 Sempre

Agradecemos as suas respostas.

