The DIVA questionnaire analyses and quantifies the impact of female genital aging. It consists of 23 items grouped into 4 constructs, which include the dimensions of daily activities, emotional well-being, sexual function, and self-esteem and body image. There are two versions of the questionnaire: the full version with 23 items, which includes 4 items on sexual function that can only be evaluated in sexually active women, and a shorter version with 19 items that can be applied regardless of sexual activity. Each item is rated on a 5-point Likert scale, with the dimension value obtained by calculating the average of the corresponding items. Higher values indicate a greater adverse impact of atrophy symptoms.

---

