3. **DIVA Questionnaire (Day-to-day Impact of Vaginal Aging):** This questionnaire assesses the impact of vaginal aging on daily life. The original version was developed by Alison J. Huang (Annex 4), Director of the Department of Medicine at the University of California, San Francisco. It included 745 postmenopausal women, from 2008 to 2012, of multiethnic backgrounds with at least one complaint of genital atrophy (dryness, burning, irritation, and itching) or pain during sexual intercourse. The questionnaire is constructed with a multidimensional scale covering 4 domains: (1) daily activities, (2) emotional well-being, (3) sexual function, and (4) self-esteem and body image. The full version consists of 23 items, with a version for women without sexual activity that includes a "not applicable" option for the sexual function domain. The items are scored between 0 and 4, and the overall score is the average of the scores in each domain, with higher scores indicating a greater impact and severity of genital atrophy symptoms. The internal consistency of the original scale in English ranged from 0.47 to 0.72, with Cronbach's alpha between 0.82 and 0.93. Confirmatory factor analysis showed appropriate structural validity with a comparative fit index of 0.987 and a standardized root mean square residual (SRMR) of 0.038. A measurement property assessment of this symptom evaluation questionnaire identified it as one of the best quality and reliable tools for assessing female genital atrophy (Annex 1 and 4).
4. **EQ-5D** is a generic instrument for measuring health-related quality of life, which generates an index representing an individual's health state. Developed by the EuroQoL group since 1987 and made public in 1990, it is based on a classification system that describes health in five dimensions: mobility, self-care, usual activities, pain/discomfort, and anxiety/depression. Each dimension has three associated severity levels: no problems (level 1), some problems (level 2), and extreme problems (level 3) experienced by the individual. Another measure used is the EQ-VAS, a 20 cm vertical visual analog scale (VAS) ranging from 0 to 100, where 0 is the worst and 100 the best imaginable health. This measure of self-perceived health is

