Never	Rarely	Sometimes	Fairly often	Very often

9. Bad about yourself?

 0	 1	 2	 3	 4
Never	Rarely	Sometimes	Fairly often	Very often

**PART C.** The following questions ask about the impact of your symptoms on vaginal sexual intercourse as well as other types of sexual activity such as self-stimulation or masturbation. During the past four weeks, have vaginal symptoms such as dryness, soreness, irritation, or itching affected:

10. Your desire or interest in having sexual intercourse or other types of sexual activity (including self-stimulation or masturbation)?

0      1      2      3      4  
Not at all      A little bit      Moderately      Quite a bit      Extremely

11. How frequently you had sexual intercourse or other types of sexual activity (including self-stimulation or masturbation)?

0      1      2      3      4  
Not at all      A little bit      Moderately      Quite a bit      Extremely

12. Your ability to become aroused during sexual activity (including self-stimulation or masturbation)?

0      1      2      3      4  
Not at all      A little bit      Moderately      Quite a bit      Extremely

Not applicable – I have not had sexual activity of any kind recently

13. Your ability to be spontaneous about sexual activity (including self-stimulation and masturbation)?

0      1      2      3      4  
Not at all      A little bit      Moderately      Quite a bit      Extremely

Not applicable – I have not had sexual activity of any kind recently

15. The amount of pleasure you experienced during sexual activity (including self-stimulation or masturbation)?

0      1      2      3      4  
Not at all      A little bit      Moderately      Quite a bit      Extremely

Not applicable – I have not had sexual activity of any kind recently

16. Your desire or interest in being in a sexual relationship?

0      1      2      3      4  
Not at all      A little bit      Moderately      Quite a bit      Extremely

17. Your confidence that you could sexually satisfy a partner?

0      1      2      3      4  
Not at all      A little bit      Moderately      Quite a bit      Extremely

18. Your overall satisfaction with your sex life?

0      1      2      3      4  
Not at all      A little bit      Moderately      Quite a bit      Extremely

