#### **Recommended scoring**

Total scores for each domain scale are computed by calculating the average of scores for the corresponding individual items. The possible score range for all domain scales is 0 to 4, with higher scores denoting greater impact of vaginal symptoms.

Two versions of the sexual functioning scale are available: 1) a short, 5-item version that can be administered to all postmenopausal women, regardless of sexual activity status; and 2) a longer, 9-item version that includes 4 additional items (12, 13, 14, and 15) that are only appropriate for women with a history of recent sexual activity.

Activities of daily living domain: items 1, 2, 3, 4, 5

Emotional well-being domain: items 6, 7, 8, 9

Sexual functioning domain (short version): items 10, 11, 12, 16, 17, 18

Sexual functioning domain (longer version): items 10, 11, 12, 13, 14, 15, 16, 17, 18, Self-concept and body image domain: items 19, 20, 21, 22, 23

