#### **Permissions**

Although the DIVA questionnaire is copyrighted, it is available without charge from the authors, and no written permission is required for its use, provided that the following conditions are followed:

- Please refer to the questionnaire using its complete name – the Day-to-Day Impact of Vaginal Aging questionnaire - and provide the appropriate citation.
- Modifications may be made without written permission. However, please clearly identify any modifications in any publications as having been made by the users. Please let the corresponding author know of any changes for our records.

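### The Portuguese DIVA form offers a not-applicable box on all nine sexual-function items, including the five meant for every woman, so inactive women can lose the short sexual-function score

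*Protocol*

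**What the plan says.** - **Protocol, Annex 1, Part C (Portuguese form).** The box "Não aplicável- não tive atividade sexual de nenhum tipo recentemente" is printed under every item from 10 to 18.
- **Protocol, Annex 4, Part C (English source).** The equivalent box appears under items 12, 13 and 15. Item 14 is not shown in the text as read. Items 10, 11, 16, 17 and 18 have no such box; item 18, for example, ("Your overall satisfaction with your sex life") offers only the 0 to 4 scale.
- **Protocol, Annex 4, Recommended scoring.** Two sexual-function scales are described: "a short, 5-item version that can be administered to all postmenopausal women, regardless of sexual activity status", and a nine-item scale that adds "4 additional items (12, 13, 14, and 15) that are only appropriate for women with a history of recent sexual activity". The item list that follows reads "Sexual functioning domain (short version): items 10, 11, 12, 16, 17, 18", which is six items, not five.
- **Protocol, Project Rationale.** Of the 23 items, four need sexual activity, and there is "a shorter version with 19 items that can be applied regardless of sexual activity".
- **Protocol, Data Collection Instruments, item 3.** A not-applicable option is mentioned for the sexual-function domain, but the items it covers are not named.
- **Protocol, Annex 4, Permissions.** Changes to the instrument are allowed without written permission, with the request: "please clearly identify any modifications in any publications as having been made by the users". The translation steps described before the Project Rationale do not mention a change to the response options.

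**The concern.** The general objective is to validate the questionnaire in peri- and postmenopausal women. Sexual activity is not an inclusion criterion, and Annex 3, question 16, asks about current activity and years without intercourse. Sexually inactive women are therefore expected in the sample, and the five-item scale exists so that they also receive a sexual-function score.

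The Portuguese form invites these women to skip exactly those items. One who ticks the box on all five has no short-scale score; one who ticks it on some has an incomplete score. No later analysis can recover answers that the form did not collect. The validity of the short scale in inactive women would then rest only on those who chose to give scores.

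The comparator loses value too. FSFI-6 is the planned convergent measure for this domain, and its desire and satisfaction items (1 and 5) have no option for absence of sexual activity. DIVA items 10, 16 and 18, on desire and satisfaction, now do.

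The missing answers may also depend on severity. Item 11 asks whether symptoms affected how often the woman had sexual activity, and a woman who stopped because of her symptoms can truthfully tick the box. The documents do not show how often this would happen.

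**Working it through.** **1. Reproduce the protocol's own count.** The domain sizes in Annex 4 (Recommended scoring) are daily living 5, emotional well-being 4, sexual function 9 (long form), and self-concept and body image 5.

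- Full version: 5 + 4 + 9 + 5 = 23, as stated.
- Short sexual-function scale: 9 − 4 (items 12 to 15) = 5, leaving items 10, 11, 16, 17 and 18. No section prints this list of five; it follows from the scoring note.
- Short questionnaire: 5 + 4 + 5 + 5 = 19, as stated in the Project Rationale.
- With the printed six-item list: 5 + 4 + 6 + 5 = 20, which does not match 19. That list also includes item 12, which the same note restricts to women with recent activity.

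**2. Compare the forms item by item.**

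| Items | Needs recent activity (scoring note) | Box in English form | Box in Portuguese form |
|---|---|---|---|
| 10, 11 | no | no | yes |
| 12, 13, 15 | yes | yes | yes |
| 14 | yes | not shown in text as read | yes |
| 16, 17, 18 | no | no | yes |

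Short-scale items with the box: 0 of 5 in English, 5 of 5 in Portuguese. Items 10, 11, 16, 17 and 18 are on both the five-item and the six-item reading, so the six-item list does not change this result.

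**3. Effect on one woman.** Domain scores are item means. Ticking the box on k of the five items leaves a mean of 5 − k items; at k = 5 there is no score. Ticking throughout Part C leaves 5 + 4 + 5 = 14 items and 3 of 4 domains. With the box on items 12 to 15 only, the form still asks an inactive woman for 23 − 4 = 19 scored items.

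**4. Effect on the sample (illustration).** The target is 230 valid tests (Population and Study Location). Both shares below are assumptions.

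Women without a short score = 230 × share inactive × share ticking throughout

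- 10% inactive, all tick: 230 × 0.10 × 1 = 23
- 50% inactive, all tick: 230 × 0.50 × 1 = 115
- 10% inactive, half tick: 230 × 0.10 × 0.5 = 11.5, about 12
- 50% inactive, half tick: 230 × 0.50 × 0.5 = 57.5, about 58

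**5. Effect on precision (illustration).** For an assumed correlation of 0.5 with a comparator, the 95% interval is tanh(atanh(0.5) ± 1.96/√(n − 3)). At n = 230 it is 0.40 to 0.59; at n = 115 it is 0.35 to 0.63. The loss of precision is modest even in the worst case. The larger problem is who is missing.

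**The case against.** The strongest reply is that a domain-wide option may have been intended: the sentence in Data Collection Instruments, item 3, can be read that way, and Annex 1 would then match it. That sentence names no items, however, and it describes the original instrument, whose own form and scoring note restrict only items 12 to 15. The domain-wide reading also contradicts the 19-item version in the Project Rationale. It remains true that the documents do not show whether the added boxes were deliberate.

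Other points stand in part:

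- **Permission.** Modification is allowed, and identification is requested in publications, which are planned from 2025. No breach is shown. What can be said is that the protocol does not mention the change.
- **Size.** The figures of 12 to 115 women are illustrative and gross. Some inactive women would leave the items blank even without the box, so the net loss is unknown. An explicit reason is also more informative than a blank.
- **Analysis plan.** Handling of missing items can properly be left to a plan not shown here. Such a plan cannot restore answers the form did not obtain.
- **Six-item list.** It sits in a reproduced third-party annex and may be inherited. The study still has to say which items it scores.

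**Conclusion.** The point holds. The Portuguese form puts the not-applicable box on all five items that the instrument reserves for every woman; the source form puts it on none of them. This rests on a direct reading of the two annexes and on an item count that reproduces the protocol's 23 and 19.

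The consequence for a woman who ticks throughout is certain: no short sexual-function score. The consequence for the sample is not known, because the documents give neither the share of inactive women nor their use of the box.

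The scope is limited. The other three domains and the 23-item version in sexually active women are unaffected. What is exposed is the claim that the short sexual-function scale works in sexually inactive women. This should be fixed, but it does not undermine the study as a whole.

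**What to change.** **If the form can still be changed**

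1. Annex 1: keep the not-applicable option on items 12 to 15 and remove it from items 10, 11, 16, 17 and 18.
2. Data Collection Instruments, item 3: state that the option covers items 12 to 15 only.
3. State in the protocol which items form the short scale, reconciling the five-item description in Annex 4 with its six-item list, and fix this before scoring.

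The cost is one reprinted questionnaire page and two text edits, plus whatever re-approval or renewed pre-testing the sites require. Some inactive women may then leave the items blank.

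**If data are already collected** (the stated end date is 22/01/2024)

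1. Declare the added option as a modification in publications.
2. Report not-applicable counts for each of items 10 to 18 by sexual-activity status (Annex 3, question 16).
3. Analyse the sexual-function domain in the women who answered it, with the short-scale items fixed beforehand as above.
4. Do not claim that the sexual-function part of the 19-item version is validated in sexually inactive women beyond those who gave scores.

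The cost is one table, a sentence declaring the change, and a narrower claim.
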